Given most studies regarding the effectiveness and safety of the early follicular phase full-dose down-regulation protocol are retrospective studies, the results may be biased by several confounding factors. Therefore, we would like to conduct a multicenter, randomized controlled trial to compare the pregnancy outcome and safety between the early follicular phase full-dose down-regulation COH protocol and the luteal phase down-regulation protocol.

Methods/Design

We will perform the multicenter, randomized controlled trial in 14 reproductive medicine centers all over mainland China. Included patients will be distributed in a 1:1 ratio to the intervention (early follicular phase full-dose down-regulation) group and the control (mid-luteal phase down-regulation) group. Their live birth rate of fresh embryo transfer and other secondary outcomes will be compared. This study has been approved by the institutional review boards at all study sites. Each participant will sign the consent form before inclusion. Reporting of the study results will follow the 2010 CONSORT statement [11].

Inclusion criteria

The following are the inclusion criteria for this study:

1. Women aged between 20 to 38 years old and with a history of infertility (fail to get pregnant after over one year's regular, unprotected sex), who receive IVF/ICSI for one of the following reasons:
 - ① Tubal factor: e.g. peritubal adhesions, tubal obstruction, etc.. Patients with hydrosalpinx can be enrolled after salpingectomy or tubal ligation;
 - ② Male factor: e.g. oligospermia, asthenozoospermia, teratozoospermia, etc.;
 - ③ Unexplained infertility: patients with a history of infertility more than 1 year but with no specific cause for infertility (ovulation, tubal, endometrial and male factor), or still not get pregnant after the above-mentioned causes being removed.
2. Women with a normal ovarian reserve according to: ① basal steroid hormone on day 2-4 of menstrual cycle: basal FSH≤10mIU/ml, estradiol (E2) <50pg/ml; ② anti-Müllerian hormone (AMH)≥1.1ng/ml; ③ antral follicle count (AFC) ≥7;
3. Women who start their first IVF/ICSI cycle;
4. Women who met the above-mentioned criteria and have given the informed consent.

Exclusion criteria

1. Women with a negative reproductive history, including a history of:
 - ① recurrent miscarriage: women with twice and more than twice spontaneous miscarriage, missed abortion, biochemical pregnancies, etc.;

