For those not receiving a fresh embryo transfer (e.g. due to OHSS), and those not achieving live birth and with surplus cryopreserved embryos, the outcome of frozen-thawed embryo transfer cycles will be followed up and recorded as well.

Outcome measurements

Primary outcome

The primary outcome of this study is live birth rate per transferred cycle, defined as delivery of any viable infant ≥ 28 gestational weeks divided by all transferred cycles.

Secondary outcomes

Secondary effectiveness endpoints will include implantation rate, biochemical pregnancy, clinical pregnancy and ongoing pregnancy. *Biochemical pregnancy* will be achieved if serum β -hCG ≥ 10 U/L. *Clinical pregnancy* is defined as the presence of an intrauterine gestational sac 28 ± 4 days after embryo transfer. Ongoing pregnancy is defined as a viable pregnancy at 10-12 gestational week. The safety endpoints will include moderate and severe OHSS, pregnancy loss, pregnancy complications, neonatal birth weight and adverse fetal outcomes (e.g. malformation, intrauterine fetal death, etc.)

Statistical analysis

Sample size and power calculation

Sample size will be calculated based on superiority test. The significance level will be set at $\alpha = 0.05$ and the statistical power will be set as $1 - \beta = 0.80$. The reported live birth rate is about 30%, while the live birth rate of the prolonged protocol is predicted to be around 40% based on previous retrospective studies. We set the delta value as 6%, and the ratio between groups will be 1:1; therefore, the sample size of each group is 851. Taking into consideration a drop rate of 10%, we expect to ultimately have a total of 1892 enrollees, with 946 participants in each group.

Statistical analysis method

1. Statistical description: We will adopt descriptive statistical analysis to summarize the participants' demographic characteristics, physical examination, laboratory tests, other health information and the outcome indicators. The continuous variables will be described with means and standard deviation (or median and interquartile range), while the categorical variable will be described with frequency and percentage. The proportion of drop-off cases will be calculated and analyzed.

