2. Comparable analysis It will be used to compare the demographic and other baseline characteristics to make sure the comparability of the two groups. If the continuous variables follow the normal distribution, t test will be performed; if not, the rank sum

test or a normal transformation will be performed. For the categorical variables, chi-square test or Fisher's exact test will be performed.

3. Statistical analysis for the outcome measures Between-group differences for categorical and continuous outcome variables will be assessed by logistic regression and linear regression, respectively.
4. Safety analysis: Adverse events and reaction will be listed and analyzed using the chi-square test.
5. The analysis for the primary outcome and important outcome measurements will be based on both the intention-to-treat analysis and per-protocol analysis. The results of these two analyses will be compared in the final analysis.

Reference

- [1] The United Kingdom national data. Human Fertility and Embryology Authority. 2015
- [2] The United States national assisted reproductive technology(ART) data. Centers for Disease Control and Prevention.2015
- [3] Chinese Reproductive Medicine Society national assisted reproductive technology (ART) data. 2015
- [4] L Hu, Y Sun. The impact of various controlled ovarian hyperstimulation (COS) protocols on the outcome of in vitro fertilization and embryo transfer (IVF-ET). *Journal of Practical Obstetrics and Gynecology*. 2014;30(10):723-725.
- [5] Y Hu, T Ding, Y Zhao, Q Wu. The comparison of the birth outcome of in vitro fertilization and embryo transfer (IVF-ET) after two different down-regulation protocols. *Maternal and Child Health Care of China*.2017;32(4):808-810.
- [6] D Xu, Q Wu. The comparison of the application of ultra-long down-regulation protocol and antagonist protocol in in vitro fertilization and embryo transfer (IVF-ET). *Jiangxi Medical Journal*. 2015;50(1):13-15.
- [7] Q Su, Q Wu, L Tian, Y Li. The clinical analysis of different controlled ovarian hyperstimulation (COS) protocols in in vitro fertilization and embryo transfer (IVF-ET). *Jiangxi Medical Journal*. 2014;49(8):723-725.
- [8] Y Li, Q Wu, Y Yi. The impact of the follicular phase ultra-long long down-regulation protocol on PCOS patients' outcome after in vitro fertilization and embryo transfer (IVF-ET). *Jiangxi Medical Journal*. 2014;49(2):117-120.

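### Safety is a stated aim, but adverse events get only a chi-square test: no effect estimate, confidence interval, denominator or small-count method, and no rule on whether item 3 or item 4 governs the named safety endpoints

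*Combined protocol and SAP*

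**What the plan says.** The title names effectiveness and safety together, and the last paragraph of the Background gives the aim as a trial "to compare the pregnancy outcome and safety" of the two down-regulation protocols.

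Under Outcome measurements, Secondary outcomes: "The safety endpoints will include moderate and severe OHSS, pregnancy loss, pregnancy complications, neonatal birth weight and adverse fetal outcomes".

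Under Statistical analysis method:

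- Item 1 covers description, including the outcome indicators: "the categorical variable will be described with frequency and percentage".
- Item 2, on baseline comparability, is the only place that names an exact test: "For the categorical variables, chi-square test or Fisher's exact test will be performed".
- Item 3, on outcome measures: "Between-group differences for categorical and continuous outcome variables will be assessed by logistic regression and linear regression, respectively".
- Item 4, on safety, reads in full after its label: "Adverse events and reaction will be listed and analyzed using the chi-square test".
- Item 5 applies intention-to-treat and per-protocol analyses to the primary and important outcomes. It does not say whether safety is included.

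The sample size section uses live birth rates only. No event rate, margin or power is given for any safety endpoint, and a confidence interval is not mentioned anywhere in the plan.

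**The concern.** A chi-square test gives a p-value. It does not say how large a difference in harm was seen, or how large a difference the data still allow. In a trial sized for a common efficacy outcome, that second quantity is what a reader needs for uncommon harms.

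Three further points are left open.

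- **Governing item.** OHSS, pregnancy loss and the other named safety endpoints are listed as outcomes, so item 3 can apply to them. They are also safety endpoints, so item 4 can apply.
- **Denominator.** OHSS can follow stimulation in any woman. The section on trigger and oocyte retrieval has all embryos frozen in women at high risk of it, so these women have no fresh transfer. If the safety tables took over the primary outcome's denominator of transferred cycles and read it as fresh transfers, those women would leave the OHSS rate. Pregnancy loss can occur only after pregnancy, and the trial expects the arms to differ in pregnancy outcome.
- **Small counts.** Item 4 gives no exact alternative, although adverse events are where sparse tables are most likely.

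**Working it through.** **Inputs from the documents.** 851 per group before allowance for dropout; 10% dropout; 946 per group and 1892 in total; significance level 0.05, sidedness not stated.

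**The plan's own figures.** The dropout step reproduces: 851 / 0.9 = 945.6, rounded up to 946, and 2 × 946 = 1892. The 851 itself does not follow from the stated live birth inputs (30% v 40% needs 356 per group and 30% v 36% needs 963, both two-sided with 80% power). That is a separate matter. Here 851 and 946 serve only as the lower and upper number of women per arm.

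**Assumptions.** A two-sided 5% test. Event rates are assumed over a range, because the documents give none.

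**Step 1: power of the chi-square test.**

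Power = Φ{ [ |p1 − p2|·√n − 1.96·√(2p̄(1 − p̄)) ] / √(p1(1 − p1) + p2(1 − p2)) }, where p̄ = (p1 + p2)/2.

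Example, 1% v 2% with n = 946: (0.3076 − 0.3369) / 0.1718 = −0.171, so power = Φ(−0.171) = 43%.

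| Assumed rates | n = 851 | n = 946 |
|---|---|---|
| 1% v 2% | 40% | 43% |
| 2% v 3% | 26% | 29% |
| 3% v 4.5% | 37% | 40% |
| 5% v 7% | 41% | 45% |
| 2% v 4% | 68% | 72% |
| 3% v 6% | 85% | 88% |
| 5% v 10% | 98% | 98% |

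Exact enumeration of the uncorrected test agrees within about 2 points. The upper four rows are more likely than not to be missed; the lower three are more likely than not to be detected.

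**Step 2: infant outcomes.** With live birth in 30% to 40% of 851 women there are about 255 to 340 births per arm (0.30 × 851 = 255; 0.40 × 851 = 340). The same formula gives 26-33% power for 2% v 4% and 57-70% for 5% v 10%.

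**Step 3: what an interval adds.** Take 9 v 17 events of 851 (1.06% v 2.00%).

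- Chi-square = (17 − 9)² / [26 × (1 − 26/1702)] = 64 / 25.60 = 2.50, so p = 0.11.
- The risk difference is 0.94 points. The Wilson limits are 0.56% to 2.00% and 1.25% to 3.18%.
- Newcombe lower limit: 0.94 − √(0.75² + 0.94²) = −0.26 points. Upper limit: 0.94 + √(1.18² + 0.50²) = +2.22 points.

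The p-value says only that the test is not significant. The interval says that an excess of about 2 per 100 women has not been excluded. Likewise, 17 v 17 of 851 gives p = 1.0, with an interval of −1.4 to +1.4 points.

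**Step 4: small counts.** Take 0 v 4 events of 946, with an expected count of 2 per arm.

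- Chi-square = 4² / [4 × (1 − 4/1892)] = 4.01, so p = 0.045.
- Fisher, two-sided = 2 × (946·945·944·943) / (1892·1891·1890·1889) = 0.125.

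The two tests fall on opposite sides of 0.05.

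**The case against.** The strongest reply is that the plan does not confine safety to a p-value. Item 1 gives counts and percentages, from which a reader can form a risk difference. The named safety endpoints are listed as outcomes, so item 3 can supply odds ratios and, for birth weight, a mean difference. Item 4 may be meant only for other adverse events. This stands as a possible reading, but the plan does not state that division, and on any reading no interval, denominator or small-count method is required.

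Three stronger readings are tempting and should not be drawn.

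- **That the test would miss most real increases in harm.** This depends on rates that the documents do not give. It fails for doublings from about 2% upwards (68-72% power at 2%, 85-88% at 3%).
- **That non-significance would be read as no difference.** The plan makes no equivalence or non-inferiority claim for safety and does not say how a non-significant result will be worded.
- **That two tests per endpoint invite reporting the more favourable one.** Unadjusted logistic regression and chi-square nearly coincide: 9 v 17 of 946 gives p = 0.120 (Wald) and 0.114. Item 3 mentions no covariates that would pull them apart.

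It is also fair to say that limited power for uncommon harms is common in trials sized for efficacy, and that intervals do not cure it.

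**Conclusion.** The point holds as a gap in method and reporting. For a stated aim of the trial, item 4 specifies a test and nothing else, and the plan does not say whether item 3 or item 4 governs the named safety endpoints.

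How much this matters depends on event rates that have to be assumed. For increases such as 1% v 2%, 2% v 3% or 5% v 7%, a non-significant result is more likely than not even when the harm is real (power 26-45%). For doublings from 2% or more, the test will usually detect it. With very few events, chi-square can give a significant result that an exact test does not support.

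These figures assume a two-sided 5% level, 851 to 946 women per arm and, for infant outcomes, live birth in 30% to 40% of 851 women. The point does not affect the primary analysis. It should be settled before the data are analysed.

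**What to change.** Rewrite item 4 along these lines:

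1. For each binary safety endpoint and each adverse event type, count each woman once and report events and women per arm with the risk difference and its 95% confidence interval (Newcombe or Miettinen-Nurminen).
2. Use Fisher's exact test where expected counts are small, and label safety p-values as descriptive.
3. Use all randomised women as the denominator for treatment harms such as OHSS. Show pregnancy loss and pregnancy complications both per randomised woman and per clinical pregnancy, because the second is conditional on something that happens after randomisation.
4. State that item 4 governs the binary safety endpoints, and that birth weight is analysed under item 3 as a mean difference with a 95% confidence interval.
5. State that a non-significant result will not be reported as equal safety.

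The cost is a short change of wording and a few more table columns. It needs no new data and no more participants. It will not raise power; it lets the reader see how much harm the trial could not exclude.
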